3.3.3. Statistical Hypotheses

The primary estimate of interest, change from baseline in total Mayo score at Week 8, is used to evaluate the effectiveness of TD-1473 therapy relative to the placebo comparator in the mITT population.

The following hypothesis testing schema will be employed to assess the primary endpoint:

The null hypothesis for the treatment comparison will be that there is no difference between the mean responses at a given dose level of TD-1473 (active) and the mean response on the placebo treatment in the change from baseline in total Mayo score at Week 8.

The alternative hypothesis will be that there is a difference.

Symbolically, this is expressed as follows:

$$H_0 : \mu_{Active} = \mu_{placebo}$$

$$H_1 : \mu_{Active} \neq \mu_{placebo}$$

In order to control for the comparison of 3 active treatment groups versus placebo for the primary endpoint, a multiplicity procedure is planned.

3.3.4. Primary Efficacy Analyses

3.3.4.1. Primary Estimand

The primary estimand uses a treatment policy strategy that considers the efficacy response in patients regardless of use of rescue medication.

Population:

The study population consists of treated subjects with moderately-to-severely active UC as defined by an adapted Mayo score between 4 and 9 with a Mayo endoscopic subscore ≥ 2 who are corticosteroid-dependent or had intolerance or demonstrate an inadequate response or loss of response to conventional therapy (aminosalicylates, corticosteroids or immunomodulators) [i.e., as azathioprine or 6-mercaptopurine] or biologics [i.e., anti-TNF-therapy, anti-integrin, or anti-IL-12/23]. Randomized and treated subjects with inclusion or exclusion protocol deviations will be included in the analysis.

Variable:

Change from baseline in Total Mayo Score at Week 8. Subjects with any of the following intercurrent events (ICE) prior to Week 8 will have data analyzed as collected following ICE under Treatment Policy approach.

Intercurrent events:

The following are the intercurrent events considered for this study:

Treatment Failure ICE:

1. Prohibited medication for UC or adverse event of worsening UC
2. Documented ostomy, colectomy or any other major intestinal resection for UC during the treatment period
3. Increase in dose of oral corticosteroids or aminosalicylates above baseline dose
4. Initiation of oral corticosteroids or aminosalicylates where they were not ongoing at baseline
5. Discontinuation of study treatment due to lack of clinical benefit or AE of worsening UC

Other ICE:

6. Discontinuation of study treatment due to COVID-19
7. Discontinuation of study treatment due to reasons other than COVID-19, lack of clinical benefit or AE of worsening UC

Population-level summary:

The mean difference in change from baseline in Total Mayo Score at Week 8 between each TD-1473 group and placebo.

3.3.4.2. Analysis Methods

The primary endpoint of change from baseline in Total Mayo Score at Week 8 will be analyzed based on the Primary Estimand by fitting an ANCOVA model incorporating the change from baseline tMS measurement at Week 8 as the dependent variable in the model. The model will include fixed-effect class terms for treatment group, prior biologic failure status (yes/no), corticosteroid use at baseline (yes/no). A covariate for baseline tMS will be included.

Summaries will be on the mITT population and include observed values, change from baseline values, and least square (LS) means estimate. For testing of the primary endpoint, each TD-1473 dose versus placebo will be compared by displaying the LS mean difference estimate to placebo and associated 95% confidence interval. Unadjusted p-values will also be reported.

A 4-group forest plot will summarize the LS mean change from baseline in Total Mayo Score at Week 8 with 95% confidence interval. An additional 3-group forest plot will summarize the difference from placebo in LS mean change from baseline in Total Mayo Score at Week 8 with 95% confidence interval. The 3-group forest plot will also display the differences from placebo

for Supplementary Estimand 1 (Section 3.3.6.1) and Supplementary Estimand 2 (Section 3.3.6.2).

Graphical inspection of the model assumptions on the primary analysis will be performed and will include inspection of equal slopes, linearity of regression, equal variances and the independence and normality of errors. In the event that the ANCOVA assumptions are not met then p-values will be generated from the nonparametric randomization-based analysis of covariance methodology of Koch et al. (1998).

3.3.4.3. Missing Data Handling

After accounting for intercurrent events and individual missing components (outlined in Section 3.3.2) all missing data (including data missing due to COVID-19) will be assumed missing completely at random (MCAR) and not imputed.

3.3.5. Sensitivity Analyses

A sensitivity analysis of the MCAR assumption for the primary endpoint will be performed where missing data will be assumed Missing at Random (MAR). Missing components of the Total Mayo Score will be imputed through multiple imputation. Details on the multiple imputation methodology are outlined in Section 5.9.

3.3.6. Supplementary Analyses

3.3.6.1. Supplementary Estimand 1

This estimand uses a hybrid strategy where subjects meeting intercurrent events for treatment failure follow a composite strategy and subjects meeting intercurrent events other than treatment failure follow a hypothetical strategy.

Population:

The study population consists of treated subjects with moderately-to-severely active UC as defined by an adapted Mayo score between 4 and 9 with a Mayo endoscopic subscore ≥ 2 who are corticosteroid-dependent or had intolerance or demonstrate an inadequate response or loss of response to conventional therapy (aminosalicylates, corticosteroids or immunomodulators) [i.e., as azathioprine or 6-mercaptopurine] or biologics [i.e., anti-TNF-therapy, anti-integrin, or anti-IL-12/23]. Randomized and treated subjects with inclusion or exclusion protocol deviations will be included in the analysis.

Variable:

Change from baseline Total Mayo Score at Week 8. Subjects meeting intercurrent events (1-5) will have their change from baseline in Total Mayo Score at Week 8 equal to zero.

Intercurrent events:

Intercurrent events outlined in Section 3.3.4.1.

Population-level summary:

The mean difference in change from baseline in Total Mayo Score at Week 8 between each TD-1473 group and placebo.

Analysis Methods:

Subjects meeting intercurrent events (1-5) follow a composite strategy with baseline observation carried forward (BOCF). Subjects affected by remaining intercurrent events follow a hypothetical strategy where data following the intercurrent event is set to missing and assumed MAR. All other missing data following application of intercurrent event strategies will be also be assumed to be MAR. For all data assumed MAR multiple imputation will be performed to generate a group of imputed datasets (n=20 imputed datasets per Mayo subscore component). Details on the multiple imputation are outlined in Section 5.9.

The following covariates will be included in the imputation model to impute the missing components: treatment group, prior biologic failure status (yes/no), corticosteroid use at baseline (yes/no) and the individual baseline Total Mayo subscore components. The tMS will then be calculated by summing together the individual components for each imputation.

The change from baseline in Total Mayo Score at Week 8 will be analyzed after applying multiple imputation using the same ANCOVA model as outlined for the primary estimand on each imputed dataset. The SAS procedure MIANALYZE is then used to combine the results from the ANCOVA analysis of each imputation.

3.3.6.2. Supplementary Estimand 2

This estimand has the same variable, analysis, ICE and population level summary as primary estimand however the population differs and is defined below.

Population:

Treated subjects who reach the Week 8 visit without any major protocol deviations and who enter the study with moderately-to-severely active UC as defined by an adapted Mayo score between 4 and 9 with a Mayo endoscopic subscore ≥ 2 who are corticosteroid-dependent or had intolerance or demonstrate an inadequate response or loss of response to conventional therapy (aminosalicylates, corticosteroids or immunomodulators) [i.e., as azathioprine or 6-mercaptopurine] or biologics [i.e., anti-TNF-therapy, anti-integrin, or anti-IL-12/23].

3.3.6.3. Subgroup Analysis

To characterize the consistency of the treatment effect for the primary and supplementary estimands, the primary endpoint analysis will be repeated for each examination group specified below.

The subgroups will be analyzed with the inclusion of an interaction term of treatment*subgroup category and baseline*subgroup category into the primary analysis model. If a subgroup determines the level of a class effect included in the primary analysis model, the redundant term will be omitted (e.g., prior biologic failure status subgroup analyses will not include the status term). Treatment group LS means for each subgroup will be calculated by setting the baseline score to the subgroup mean (for the subjects included in the analysis).

The following subgroups are pre-defined:

- Biologic Failure Status: [a] Yes, [b] No

- Biologics experience categories: [a] Primary non-responder, Secondary non-responder or intolerant, [b] naïve, [c] bio-experienced [but not documented failure]
- Number of prior biologics failed [a] 0 [b] 1 [c] ≥ 2
- Number of biologic classes failed [a] 0 [b] 1 [c] ≥ 2
- Inadequate response to at least one biologic: [a] Yes, [b] No
- Intolerant to at least one biologic: [a] Yes, [b] No
- Steroid use status at enrollment: [a] Yes, [b] No
- Baseline Tobacco use Status: [a] no use [b] prior use [c] current use
- Extent of disease: [a] Proctosigmoiditis, [b] Left-sided colitis, [c] extensive
- Duration of disease: [a] ≤ 5 years, > 5 to ≤ 15 years, > 15 years

■ [REDACTED]

■ [REDACTED]

- Baseline total Mayo score: [a] ≤ 10 [b] > 10
- Baseline adapted Mayo score: [a] ≤ 7 [b] > 7
- Baseline Mayo Endoscopy subscore [a] 2 [b] 3
- Baseline Rectal Bleeding subscore [a] 0 [b] ≥ 1
- Geographic Region: [a] North America [b] Eastern Europe [c] Europe (excluding Eastern Europe) [d] Asia/Pacific [e] Other;
- Country: [a] Japan [b] United States [c] Rest of the world
- Refractory or intolerant to 6-MP/AZA: (yes, no)
- Refractory, dependent or intolerant to oral or IV corticosteroids: (yes, no)
- Evidence of inadequate response, recurrent disease or relapse to 6-MP/AZA OR corticosteroids: [a] yes to both, [b] No to 6-MP/AZA and yes to steroids, [c] yes to 6-MP/AZA and no to steroids, [d] No to both

3.3.6.4. Total Mayo Score Component Analysis

Summaries of each individual Total Mayo Score component will be presented by treatment group and visit over time. The components will be presented as both a continuous and categorical variables separately, displaying summary statistics and then a shift table for percentage of subjects with each score (0, 1, 2, 3) at baseline and Week 8.

3.3.6.5. Total Mayo Score Completeness and Intercurrent Event Summaries

Summaries of the completeness of Total Mayo Score components at Week 8 will be performed where the number of patients missing 1, 2, 3 or all components will be presented. For subjects with all components missing the summary will be further broken down by those of discontinue prior to Week 8 and those who missed the Week 8 visit.

The number of subjects who experience an intercurrent event prior to Week 8 and those who don't will also be presented for the subset of subjects with at least one Total Mayo Score component missing at Week 8.

An analysis of all subjects who experience an intercurrent event will also be performed where the number of subjects overall who experience an ICE and the number who experience each specific ICE criteria will be presented.

3.4. Secondary Endpoint(s) Analyses

3.4.1. Key Secondary Endpoint

The key secondary endpoint is:

- Clinical remission by adapted Mayo score components at Week 8

3.4.2. Statistical Hypotheses

The key secondary estimate of interest, clinical remission by adapted Mayo score components at Week 8, is used to evaluate the effectiveness of therapy relative to the placebo comparator in the mITT population.

The following hypothesis testing schema will be employed to assess the secondary endpoint:

The null hypothesis for the treatment comparison will be that there is no difference between the proportion of subjects in remission at a given dose level of TD-1473 (active) and the proportion of subjects in remission on the placebo treatment.

The alternative hypothesis will be that there is a difference.

Symbolically, this is expressed as follows:

$$H_0: P_{Active} = P_{placebo}$$

$$H_1: P_{Active} \neq P_{placebo}$$

In order to control for the comparison of 3 active treatment groups versus placebo for the secondary endpoint, a multiplicity procedure is planned (See Section 3.6).

3.4.3. Definition of Key Secondary Endpoint

The adapted Mayo score (0-9 points) is the sum of three components: stool frequency (0-3 pts), rectal bleeding (0-3 pts), and Mayo endoscopic (0-3 pts) subscores.

Clinical remission by Adapted Mayo Score requires each of the subscores to meet the criteria defined in [Table 6](#). If at least one component of the adapted Mayo score (aMS) is available then the score will be calculated. Missing components will be imputed through last observation carried forward.

Table 6: Clinical Remission by aMS Definition

Mayo Definition	Stool Frequency	Rectal Bleeding	Endoscopic Findings
Adapted Mayo Score (aMS)	0 or 1	0	0 or 1

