- Change in total Mayo score from baseline at Week 8

Key Secondary (with multiplicity control):

- Clinical remission by adapted Mayo score at Week 8

Phase 3 Induction Primary and Key Secondary Efficacy Endpoints (with multiplicity control) in order of testing:

Primary:

- Clinical remission by adapted Mayo score at Week 8

Key Secondary:

- Endoscopic healing at Week 8
- Symptomatic remission at Week 8
- Clinical response by adapted Mayo score definition at Week 8
- Mucosal healing at Week 8
- Deep symptomatic remission at Week 8

Phase 3 Maintenance Primary and Key Secondary Efficacy Endpoints (with multiplicity control) in order of testing:

Primary:

- Clinical remission by adapted Mayo score at Maintenance (m)Week 44

Key Secondary:

- Maintenance of clinical response at mWeek 44
- Endoscopic healing at mWeek 44
- Symptomatic remission at mWeek 44
- Corticosteroid-free remission at mWeek 44
- Maintenance of clinical remission at mWeek 44 in those who were in remission at mWeek 0
- Mucosal healing at mWeek 44
- Deep symptomatic remission at mWeek 44

Refer to [DEFINITION OF TERMS](#) for detailed definition of primary and key secondary endpoints

Safety Endpoints:

Incidence and severity of treatment-emergent adverse events; changes in laboratory test results, ECG intervals and abnormalities, and vital sign measurements

Analysis:

In general, binary endpoints will be analyzed using Cochran-Mantel-Haenszel tests, stratifying by randomization stratum. Subjects with missing binary outcomes will be counted as not meeting the endpoint for analysis purpose. Logistic regression models may be fitted for selected endpoints to evaluate dose-response curves.

Continuous endpoints will be analyzed by fitting mixed effect or analysis of covariance models which include terms for treatment, stratification factors, and baseline score.

The primary analysis set for efficacy endpoints will be a modified intent-to-treat (mITT) set comprising all subjects who receive at least one dose of study drug, summarized by randomized treatment.

For each Study, the family-wise type 1 error rate for primary and key secondary endpoints included in the statistical testing hierarchy will be controlled at 5% by use of a gatekeeping procedure with a pre-specified testing sequence. All comparisons will be 2-sided.

Safety data will be summarized by actual treatment received using frequency of events or descriptive summary statistics, as appropriate.

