8.9. Data Handling Rules

For primary analyses of all applicable efficacy endpoints, including secondary and additional endpoints, the following rules will be applied. For sensitivity analyses of primary and key secondary endpoints, different rules may be specified in the applicable SAP.

- Binary endpoints: Subjects who had non-missing data for a binary efficacy endpoint meeting the criterion for success but met definition of treatment failure prior to visit will be considered as not meeting endpoint. Full rules for the derivation of treatment failure will be outlined in the SAP.
- Missing = endpoint not met

Quantitative or score endpoints:

- The treatment failure criteria above are applied to exclude any assessments obtained following treatment failure
- MMRM analysis with data assumed to be “Missing at Random” for quantitative or score endpoints assessed more than once postbaseline
- The analysis of the Phase 2b primary endpoint will be a completers analysis. For other quantitative or score endpoints assessed only once post-baseline, imputation for missing data will be described in the SAP.

[REDACTED]

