3.4.4. Key Secondary Efficacy Analyses**3.4.4.1. Estimands**

Clinical remission by adapted Mayo Score will be analyzed through a composite strategy as follows:

- Population: Same as primary estimand
- Variable: Endpoints (Section 3.4.1) and Definition (3.4.3). Subjects meeting criteria for ICE, with the exception of ICE criteria 6, will have their remission status at Week 8 set to not in remission.
- Intercurrent Events: Intercurrent events outlined in Section 3.3.4.1.
- Population-level summary: The difference in proportion in clinical remission by adapted Mayo Score between each TD-1473 group and placebo.

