3.4.4.3. Missing Data Handling

Following the application of ICE strategy, missing data will be imputed as not in remission .

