3.3. Primary Endpoint(s) Analysis

3.3.1. Definition of Primary Endpoint

The primary endpoint is:

- Clinical remission by adapted Mayo score components at mWeek 44

The adapted Mayo score (0-9 points) is the sum of three components: stool frequency (0-3 pts), rectal bleeding (0-3 pts), and Mayo endoscopic (0-3 pts) subscores.

Clinical remission by adapted Mayo score requires each of the subscores to meet the criteria defined in [Table 4](#). There will be no imputation of missing components, if a component is missing then the endpoint is missing.

Table 4: Clinical Remission by aMS Definition

Mayo Definition	Stool Frequency	Rectal Bleeding	Endoscopic Findings
Adapted Mayo Score (aMS)	0 or 1	0	0 or 1

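### Phase 2b SAP 3.4.3 lets carried-forward diary scores make a Week 8 remitter, and does not say whether this precedes the rule that missing data count as not in remission

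*SAP*

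**What the plan says.** **Phase 2b SAP.** Section 3.4.3 first sets the criterion: "Clinical remission by Adapted Mayo Score requires each of the subscores to meet the criteria defined in" Table 6 (stool frequency 0 or 1, rectal bleeding 0, endoscopy 0 or 1). It then gives the component rule: "If at least one component of the adapted Mayo score (aMS) is available then the score will be calculated", and "Missing components will be imputed through last observation carried forward". Section 3.4.4.1 takes the estimand's variable from 3.4.3, so LOCF is part of the endpoint definition. Section 3.4.4.3 adds that, once the intercurrent-event strategy has been applied, "missing data will be imputed as not in remission". Section 3.4.5 plans no sensitivity analysis for this endpoint.

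**Diary scores.** Phase 2b SAP 5.4.1 uses the 7 days before the visit, drops preparation days, the endoscopy day and the day after, and treats the score as missing if 3 days cannot be found.

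**Protocol.** The synopsis, under Analysis, says: "Subjects with missing binary outcomes will be counted as not meeting the endpoint for analysis purpose". Section 8.9 has "Missing = endpoint not met" for the primary analyses of all applicable efficacy endpoints, secondary ones included. It says the SAP may specify different rules for sensitivity analyses.

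**Maintenance SAP.** Section 3.3.1, for the same remission definition: "There will be no imputation of missing components, if a component is missing then the endpoint is missing".

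**The concern.** The two SAP rules pull in opposite directions. One completes a partly observed score with older values; the other counts missing data as failure. If completion comes first, the failure rule reaches only subjects with nothing left to calculate from, and an earlier symptom score stands in for an absent Week 8 one. If the failure rule is meant to prevail, 3.4.3 has no purpose for remission. Two programmers could derive different remission counts from this text.

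Remission at Week 8 is the only key secondary endpoint under multiplicity control in Phase 2b, and protocol 8.11 names it in the dose-selection steps. The Maintenance SAP introduction reports that the programme stopped for lack of Phase 2b efficacy, so dose selection is past. What remains at stake is the reported remission rates and their comparisons with placebo.

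**Working it through.** **1. The plan's own figure.** No power is stated for remission in Phase 2b. The stated figure is for the total Mayo score (60 per arm, 2-point effect, Hochberg at 5% two-sided). Simulation with 200,000 runs, three doses against a shared placebo, gives:

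| SD | All three doses, stated | Simulated | At least one, stated | Simulated |
|---|---|---|---|---|
| 3 | 89% | 88.9% | above 98% | 98.4% |
| 3.5 | 73% | 73.9% | 94% | 93.9% |

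These figures reproduce and are not in dispute. The 60 per arm is used below.

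**2. Which carried components can produce remission.** Eligibility requires endoscopy 2 or 3 and an adapted Mayo score of 4 to 9.
- With endoscopy 2, stool plus bleeding must be at least 2: 16 − 3 = 13 states.
- With endoscopy 3, the sum must be at least 1: 16 − 1 = 15 states.
- The total is 28, and none has endoscopy 0 or 1. The only endoscopy before Week 8a is the screening one, so a carried endoscopy cannot give remission. The route is through the diary components.
- One eligible state (stool 1, bleeding 0, endoscopy 3, total 4) already meets both diary criteria. Such a subject could count as a Week 8 remitter with no diary data after baseline.

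**3. The same subject under each rule.** Week 4 stool 1 and bleeding 0; Week 8 endoscopy 1; no usable Week 8 diary; no intercurrent event.
- SAP 3.4.3 applied first: 1, 0, 1, so in remission.
- Any missing component counted as failure: not in remission.
- Maintenance SAP rule: missing, not imputed.

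**4. How a diary gap arises.** If preparation, endoscopy and the following day are one day each and all fall in the window, 7 − 3 = 4 days remain. Two further missed entries leave 2, below the 3 needed. If the visit starts on the endoscopy day, only the preparation day is lost: 7 − 1 = 6 remain, and four missed entries are needed.

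**5. Size.** One subject is 1/60 = 1.7 percentage points. For illustration only, the Phase 3 Induction planning rates (protocol 8.2.2) give 60 × 0.095 = 5.7 and 60 × 0.235 = 14.1 remitters.

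Added remission = (share of the arm with a Week 8 endoscopy but under 3 diary days) × (probability that the completed score meets remission). Neither input is in the documents. Assumed ranges of 2% to 10% and 9.5% to 50% give:
- low: 0.02 × 0.095 = 0.19 points (0.1 of 60 subjects);
- high: 0.10 × 0.50 = 5.0 points (3 of 60 subjects).

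**6. Sensitivity of the test.** Unstratified Mantel-Haenszel chi-square = (a − m/2)² / V, where a is the active-arm count, m the total remitters and V = n²m(N − m)/[N²(N − 1)], with n = 60 and N = 120.

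| Active vs placebo | Chi-square | p |
|---|---|---|
| 14 vs 6 | 16 / 4.20 = 3.81 | 0.051 |
| 15 vs 6 | 20.25 / 4.37 = 4.64 | 0.031 |
| 14 vs 7 | 12.25 / 4.37 = 2.80 | 0.094 |

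The starting pair is near 0.05, and the test is neither stratified nor adjusted for multiplicity. It shows only that one reclassified subject can matter.

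**The case against.** **The protocol is less explicit than it looks.** A reader might infer that the SAP plainly breaches the protocol. Neither the synopsis nor 8.9 says when a three-part composite with one absent part is missing. Protocol 8.1 falls back to the 3 most recent evaluable diary days without restating the 7-day limit, and read literally that could reach older days. The definitions section shows only its heading in the public copy and part of 8.9 is blacked out, so a component rule may exist there. This stands as a limit. Even so, protocol 6.4.2.1 confines diary data to the week before the visit, SAP 5.4.1 declares the score missing, and the visible protocol text contains no component LOCF.

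**The order is inferred.** Section 3.4.4.3 could be meant to override 3.4.3. That cannot be excluded, but it does not say so, and the parallel text for the primary endpoint (SAP 3.3.4.3) places component imputation before missing-data handling.

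**The group is narrow.** A reader might infer that endoscopy days routinely empty the diary window. They do not: missed entries are needed as well, and diary completion is reviewed at each visit. Subjects with intercurrent events 1 to 5 or 7 are already set to not in remission. SAP 3.4.6.3 will tabulate missing components, though not their effect on the result.

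**Two supporting arguments are weak.** The Maintenance SAP is an abbreviated, descriptive plan for a stopped study, so its different rule is no benchmark. Nor is LOCF hidden: protocol 8.1 asks that changes be described in the SAP, and 3.4.3 describes it, although Appendix 1 does not list it as a change.

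**Conclusion.** The point holds in limited form. As written, 3.4.3 allows a subject without usable Week 8 symptom data to be a Week 8 remitter, against the plain sense of the protocol's non-responder rule and in unresolved tension with SAP 3.4.4.3. This rests on LOCF being applied first, which is the natural reading but not a stated one.

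Relative to a non-responder rule, LOCF can only add remitters. A reader might infer that it favours active treatment; the documents do not support that, since carried values can add remitters in any arm. The total effect cannot be computed. The range of 0.2 to 5.0 points per arm follows entirely from assumed inputs; the firm figure is 1.7 points per subject. This should be corrected because no planned analysis would show its effect, not because a large distortion has been demonstrated.

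**What to change.** In Phase 2b SAP 3.4.3, remove component LOCF from the main remission analysis and state that a subject with any missing Week 8 component is not in remission. Keep the handling of intercurrent event 6 (discontinuation due to COVID-19) as specified in 3.4.4.2. Report the LOCF version as a sensitivity analysis and amend 3.4.5 accordingly.

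The cost is one sentence and one additional table. The drawback is that remission rates may be slightly lower, because some subjects who were in remission but missed diary entries will count as failures.
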